We seek to make an effective psychoeducation program widely available to family caregivers of persons living with Alzheimer's disease and related disorders. Taking advantage of the growing use of and familiarity with the internet by persons of caregiving age, the project will advance us toward that goal. We will test the program in an established context of collaboration among the Outreach, Recruitment, and Education Cores of four NIA-supported Alzheimer's Disease Centers (ADC). We will employ a wait-list randomized design in which 18 blocks of 15 caregivers each will be assigned either to immediate Tele-Savvy participation groups or to attention control or usual care groups that are invited to participate in Tele-Savvy six months after baseline data collection (total n=270). We will pursue 3 aims::

Aim 1. Establish the effectiveness of Tele-Savvy in reducing or retarding the affective impact (burden, depression, anxiety) on caregivers associated with dementia family caregiving

Aim 2. Establish the effectiveness of Tele-Savvy in promoting the quality of life of persons with Alzheimer's (agitation; Quality of Life; affect) whose caregivers are trained by Tele-Savvy

Aim 3. (a) Establish the effectiveness of Tele-Savvy in enhancing caregiver mastery and (b) test the mediating effect of mastery and enactment on Aim 1 & 2 outcomes

We also propose, as an Exploratory Aim, to examine the comparability of the program's efficacy across three racial/ethnic groups (African Americans, Caucasians, and Latino/Hispanics).

Significance and Innovation.

The Landscape. Dementing conditions, including the most prevalent of these, Alzheimer's disease, pose a large and growing problem nationally and worldwide. Unless dramatic breakthroughs occur, the current population of 5.3 million persons living with these conditions will swell to at least 14 million by 2050.¹ These persons are distributed across the landscape, in inner cities, in suburban areas, and in rural America; there is even some evidence that the current and future prevalence of Alzheimer's in rural areas is disproportionate to the rural population's share of the overall population.²⁻⁴ Care for these persons is costly. Total estimated cost of care in 2015 will be \$216 Billion; by 2050, it could exceed \$1 Trillion.¹

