Tele-Savvy. Tele-Savvy engages groups of (on average) six dementia family caregivers in a program that extends over 43 days (see figure below). The program begins with a scheduled 75-minute group videoconference led by one or two facilitators; similar group videoconferences then take place each of the next six weeks (i.e., seven video-conferences). In between the video-conferences, caregivers receive daily emails with links to 5-20 minute on-line video lessons that they can watch on their own schedule and as often as they wish (there are 36 unique video lessons; the Tele-Savvy story board (Appendix A) delineates the content of these video lessons). The curriculum includes all of the elements of SCP plus material from an advanced program (SCP-II)⁹⁶ and from Co-PI [name]' caregiver self-care projects (see below). The videoconferences incorporate the coaching/debriefing feature of SCP to allow caregivers to report enactment of learned and self-developed management strategy behaviors into their own caregiving. The videoconferences include talks and exercises and also allow caregivers to raise questions. Each daily video presents a teaching point linked to the overall curriculum. All follow the same format: experts provide instruction about a topic, and the lesson is carried forward by brief, scripted talks by other experts or is enacted in brief vignettes in which a fictional family caring for a father living with Alzheimer's demonstrates – at various stages of the illness – effective caregiving techniques linked to the day's teaching points.

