Monthly team videoconferences will be conducted to discuss project progress, recruitment, data collection and analysis, and other issues. The Emory coordinating team will meet weekly. The site co-

investigators and [name] will also meet annually at the ADC Directors' meeting. Additional Data Safety Monitoring Board committee meetings will be held mid-year in years 2 and 3.

Scientific Approach

Design. We aim to enroll 375 subjects in 25 cohorts of 15 subjects each, starting in project month 9 (see project timeline). We expect to enroll, on average, four cohorts per quarter through project year 2 1/2. Recruitment of every 2 cohorts (30 participants total) is scheduled to take place every 6 weeks. We will use a three-arm design with participants randomly assigned on a 2:2:1 ratio to immediate participation in the Tele-Savvy intervention (N=108), immediate participation in an attention control condition (Healthy Living) (N=108), and a usual care condition (N=54). There will be five data-collection points evenly spaced across 12 months. Those in each cohort's intervention condition will take part in Tele-Savvy immediately following baseline data collection. Those in the attention control and usual care conditions will take part in Tele-Savvy after a delay of 6 months (following the 6-month data collection point). Below, we describe the preparation activities in which we will engage (facilitator training and material revisions) and then describe the trial itself. Four NIA-supported Alzheimer's Disease (Research) Centers will collaborate in recruitment, and Emory University will serve as the coordinating center. Emory will be responsible for randomization of subjects (recruits from all sites will be pooled together for randomization), for delivery and fidelity monitoring of the intervention and attention control condition, and for all data gathering and analysis.

Please see the added document for Amendment 8.

Project Timeline, by Quarters

Main Project Activities	Year 1				Year 2				Year 3				Year 4			
	1	2	3	4	1	2	3	4	1	2	3	4	1	2	3	4
Staffing; Training; Finalizing																
DSMB scheduled meetings		X			X				X				X			X
Enroll 18 cohorts (15 each) + Acquisition	30	60	90	120	150	180	210	240	270							
Data Collection																
Data Cleaning and Analysis																
Dissemination																

Preparation.

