meta-analyses. With a final expected sample size of 215 (86, 86, 54 in Tele-Savvy (TS), attention control (AC), and usual care (UC) groups respectively), for the primary intervention test (group-by-time effect) comparing the outcomes of the three group changes from T1 to T2 to T3 (3-by-3 repeated measures design of three groups measured at three time points), at 80% power and 5% significance level, small-to-moderate effect sizes, Cohen's $f = 0.21-0.24$ may be detected for the main effects for group, time and group-by-time interaction effects (given moderate correlation between measurement pairs of $r=0.3-0.5$) (power analysis using PASS 14 Power Analysis and Sample Size Software (2015). NCSS, LLC. Kaysville, Utah, USA, ncss.com/software/pass). After adjusting for any potential group differences, the overall intervention effect of the Tele-Savvy program for the combined T1-to-T3 pre-post effects for the immediate Tele-Savvy group plus the T3-to-T5 pre-post effects from the AC and UC groups will yield a total estimated 215 subjects to perform a pre-post test to detect a small effect size of $d=0.19$ at 80% power and 5% significance level. With the pooled sample, we will be able to also test the mediating effects of mastery and self-efficacy on the Tele-Savvy program for the caregiver outcomes. As shown by Fritz and MacKinnon (2007), sample sizes of 148-196 were adequate to achieve 80% power to detect small-to-moderate effect sizes for the indirect effect of the independent variable on the dependent variable through the mediating variable considering both the Sobel test as well as percentile and bias-corrected bootstrapped approaches.¹⁰⁸ Although our analytic strategy is robust to missing data we will enroll 270 CGs (108 for TS and AC groups and 54 for UC group) per consideration 1 above (maximize accommodation) allowing for an expected 20% attrition. For the exploratory aim comparing the program's efficacy across the 3 ethnicity groups, with an expected final sample size of 215 subjects and proportions of approximately 65% Caucasian, 20% African American, 15% Hispanic, at 80% and 5% level of significance, we will be able to detect moderate effect sizes Cohen's $f=0.19-0.23$ (for 3-group by 2-time point RM-ANOVA for group, time and group-by-time effects).

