Care Recipient Mood	Neuropsychological Inventory Questionnaire	12 item inventory assessing severity of mood states or behaviors reflecting mood	Test-retest correlations between total symptom and distress scores in 15 subjects were 0.80 and 0.94, respectively (P< 0.0001 for both). ¹²¹

Data Collection. Data will be collected at baseline and at four subsequent points (months 3, 6, 9, and 12). Each data collection event will follow the same procedure used with the baseline interviews. The Navigator will establish the appointment for the Vidyo interview, and the research specialist, blinded to condition, will conduct the interview. The data collection schedule allows for a direct comparison of outcome measures between groups (at 3 and 9 months); it allows for an examination of prolonged effects (at 9 and 12 months) in the immediate participation group; and it allows for pooling of data across both groups to examine the mediating effects of mastery on distal outcomes in caregivers and PLWD and to compare effects across racial/ethnic groups. Qualitative evaluation interviews will occur at T2 and T3 for a sub-sample of immediate and T4 and T5 for a sub-sample of attention control subjects.

III. G. Variables and Measures. The table above delineates the battery of standardized instruments we will employ; these have well-established psychometric properties (reliability, validity), are used extensively with dementia caregivers, and have been used previously in the *Savvy Caregiver* trials.

As depicted in the figure below, there is a link between our theoretical model and the measures used to test it. Most data will be gathered through the regular interviews, some data will be obtained from self-reported evaluations that caregivers will complete through forms posted on the Canvas site (for example, through logs on the Canvas site in which caregivers report caregiving behaviors they have enacted). After each program, caregivers will be asked, in phone or Vidyo interviews conducted by project investigators, to evaluate the program, indicating what they did/did not like, what did/did not work, how the intervention was helpful or not, and how they would change it. Blackboard will allow us to monitor adherence, dosage and intensity of the

[figure not shown]

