data captured at T1-T2-T3 for the delay group will also be used to evaluate any potential decline occurring during this time period. All model assumptions will be tested; grand mean centering used to help combat multicollinearity between variables; and standard diagnostic tests and influence statistics used to test the distributions of the residuals. MLM models utilize all available data for all participants at each time point and have the advantage of adjusting for the missing data over time, where repeated measures ANOVAs do not. Further covariate predictors of missingness over time will be included to additionally adjust for these confounders¹²⁴ To aid in final interpretation we will include the 95% confidence intervals around means by intervention group and time period. SPSS v.22 will be used for all analyses at the 5% significance level.¹²²

Aim 3(b). To test the mediating effect of mastery on Aim 1 & 2 outcomes, we will employ the PROCESS add-on module for SPSS¹²⁵ which includes performing the combined approaches of Baron and Kenney, the Sobel test, as well as semi-parametric estimation and testing of the Sobel test through bootstrapping. The focus will be on both the immediate (T2 for immediate Tele-Savvy group and T4 for attention control and usual care groups pooled together) and sustained (T3 for immediate Tele-Savvy group and T5 for attention control and usual care groups pooled together) effects of Tele-Savvy on the mediating measure of mastery on the Aim 1 and Aim 2 outcomes of caregiver burden, depression, anxiety, and dyadic relationship and PLWD BPSD, agitation, mood, and quality of life. These indirect/mediation effects will also be tested and evaluated using structural equation modeling via AMOS v.22.¹²⁶

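### Aim 3(b) tests mediation only at visits when every arm has had Tele-Savvy and defines no exposure, so it cannot show that the programme works through mastery

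*Combined protocol and SAP*

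**What the plan says.** The Aim 3(b) paragraph of the Data Management and Analysis Plan sets the immediate analysis at "T2 for immediate Tele-Savvy group and T4 for attention control and usual care groups pooled together" and the sustained analysis at "T3 for immediate Tele-Savvy group and T5 for attention control and usual care groups pooled together". It describes the target as "effects of Tele-Savvy on the mediating measure of mastery" and on to the Aim 1 and 2 outcomes. It names a mediator, outcomes and software, but no independent variable, contrast or coding.

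Other sections confirm that pooling is intended. Power Analysis and Sample Size Determination states "With the pooled sample, we will be able to also test the mediating effects of mastery and self-efficacy on the Tele-Savvy program", and Data Collection gives as one purpose of the schedule "pooling of data across both groups to examine the mediating effects of mastery on distal outcomes".

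On timing, the Tele-Savvy section describes a "program that extends over 43 days". Under Design, the immediate arm starts straight after baseline, while the attention control and usual care arms "will take part in Tele-Savvy after a delay of 6 months (following the 6-month data collection point").

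The mediators are named three ways. The Aims page promises to "test the mediating effect of mastery and enactment on Aim 1 & 2 outcomes", the power section names mastery and self-efficacy, and the Aim 3(b) paragraph names mastery alone.

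**The concern.** A mediation claim needs an estimate of what the programme does to the mediator, which requires people with and without the programme. At T2/T4 and T3/T5 everyone has been through it. The analysis could therefore miss a real mechanism or report one that is only change over time. Aim 3(b) is half of a stated aim and carries the theory that mastery links caregiving management to outcomes.

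The scope is limited. The randomised three-arm comparison over the first three visits (Aims 1, 2 and 3(a)), which includes mastery as an outcome, is not affected.

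**Working it through.** **1. Exposure at the visits named.** Visits fall at months 0, 3, 6, 9 and 12 (Data Collection).

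| Arm | Programme starts | Visits used in Aim 3(b) | Had Tele-Savvy? |
|---|---|---|---|
| Tele-Savvy | after T1 (month 0) | T2, T3 (months 3, 6) | yes |
| Attention control | after T3 (month 6) | T4, T5 (months 9, 12) | yes |
| Usual care | after T3 (month 6) | T4, T5 (months 9, 12) | yes |

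**2. Possible readings of the undefined exposure X.**
- *Receipt of Tele-Savvy.* X = 1 for all, so the design matrix [1, X] has rank 1 and the path from X to mastery cannot be estimated.
- *Original arm.* Treated are compared with treated. If effects are similar across arms and periods, the expected path to mastery is about zero. Arm is also tied to time in study (month 3 against month 9).
- *Before/after within person.* This is estimable, but mediation cannot be separated from change over time.
- *Viewing dose or attendance.* These are recorded and vary, but they are not named as X and are not randomised.

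**3. The plan's own figure.** For a one-group pre-post test at n = 215, two-sided 5%, 80% power: d = (1.960 + 0.842)/√215 = 0.191. The stated 0.19 reproduces, but only as an uncontrolled one-group test. The 148–196 quoted for mediation comes from a cited study whose path sizes the plan does not give, so it cannot be reproduced. It also presumes an X that varies.

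**4. Sample sizes.** The text gives several: 270 × 0.80 = 216 (stated as 215); 270 × 0.75 = 202.5, using the 25% attrition under Limitations and Challenges; and 375 × 0.80 = 300, using the enrolment under Design. Split 2:2:1, these give 81/81/40, 86/86/43 and 120/120/60.

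**5. Simulation.** There were 2,000 runs per case, with a Monte Carlo interval for the indirect effect and adjustment for baseline. Simulation error is about 1 point; other seeds fell within about 4. Assumed: within-person correlation 0.5 (the upper end of the plan's 0.3–0.5), mastery gain in SD, mastery-to-outcome path, and drift in SD. AC is attention control and UC is usual care.

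| X | Assumed truth | n = 202 | n = 215 | n = 300 |
|---|---|---|---|---|
| Arm, pooled visits | gain 0.3 / 0.5, path −0.4, no drift | 4.3 / 4.5% | 4.5 / 4.4% | 4.2 / 4.6% |
| Before/after | no effect, drift 0.10, path −0.2 / −0.4 | 21.9 / 29.7% | 22.9 / 29.8% | 36.6 / 41.0% |
| Before/after | no effect, drift 0.20, path −0.2 / −0.4 | 64.5 / 81.5% | 68.3 / 82.5% | 86.5 / 92.3% |
| Randomised arm, T1–T3, vs AC / vs UC | gain 0.3, path −0.4 | 59.4 / 43.2% | 62.3 / 44.7% | 77.2 / 59.8% |
| same | gain 0.5, path −0.4 | 94.9 / 84.8% | 96.9 / 86.9% | 99.6 / 95.1% |
| same | gain 0.3, path −0.2 | 45.3 / 30.6% | 47.3 / 31.7% | 69.0 / 53.3% |
| same | gain 0 | 4.4–5.5% across sizes | | |

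A simpler model (n = 215, Sobel test, no baseline adjustment) agrees. With arm as X, true gains of 0.3–0.55 and a path of 0.4, the mean estimated path to mastery lies between −0.006 and 0.002, and rejection is 3.2–4.0%. With no programme effect but mastery drift of 0.1 or 0.2 SD per three months, rejection is 26% or 79%. The randomised T2 contrast stays at 3.6% under the same drift.

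**The case against.** The strongest reply is that the Aims 1, 2 and 3(a) paragraph defines immediate effects as the change from cT1 to cT2, and cT1 precedes the programme in every arm. On that reading the pooled data do hold each person's untreated value. This stands as a matter of wording: the absence of any untreated comparator is exact only for the visits Aim 3(b) names. On the within-person reading, what is missing is a concurrent untreated group. Aim 3(b) does not state that reading, and it remains confounded with time.

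Second, Aim 3(a) already gives a randomised test of the programme's effect on mastery. That is true, but the plan never joins it to the mastery–outcome path, so it supplies no mediation test.

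Third, the false-positive rates depend on favourable drift, while the plan also expects possible decline. At n = 215, adverse drift of 0.10 SD gives about 0% false favourable mediation, with 18–30% of runs significant in the harmful direction. At correlation 0.3, favourable drift gives 19–23%. Likewise, the 4–5% for arm assumes no drift. These figures illustrate the problem and do not predict its size.

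Fourth, the replacement has limited power and does not remove confounding between mediator and outcome. That stands, and it is costed below.

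Finally, Design refers to a separate Amendment 8 document, and a figure in Variables and Measures could not be seen. The amendment may explain 375 against 270, which is why three sample sizes are shown.

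**Conclusion.** The concern holds and must be fixed. From the schedule alone, every observation named in Aim 3(b) follows Tele-Savvy, and no reading of the unstated exposure isolates an effect of the programme through mastery. That conclusion needs no assumed effect size.

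The consequences, under the stated assumptions, run both ways. With arm as X and no drift, a true mechanism is detected no more often than the 5% error rate. With before/after as X, favourable drift of 0.10 SD alone yields apparent mediation in 22–41% of trials. A null result would therefore not count against mastery, and a positive one would not count for it.

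**What to change.** 1. **Must fix.** Rewrite Aim 3(b) on the randomised T1–T3 data in one three-arm model.
   - X is randomised arm (Tele-Savvy vs attention control; Tele-Savvy vs usual care).
   - The mediator is T2 mastery adjusted for T1.
   - The immediate effect uses the T2 outcome adjusted for T1, noting that mediator and outcome are then concurrent. The sustained effect uses the T3 outcome adjusted for T1.
   - State that mediator–outcome confounding remains despite randomisation and is strongest for the concurrent T2 analysis.
   - Name the mediators once. If enactment is kept and taken from Canvas logs, say that usual care is not introduced to Canvas until after month 6, so that mediator has no usual-care comparison over T1–T3.
   - The pooled treated-only analysis may stay as a descriptive mastery–outcome association.
2. **Should fix.** Label the pooled cT1–cT3 result uncontrolled and supportive, or enter the wait-list T1–T3 period as control time. Do not present d = 0.19 as power for a controlled effect. With no effect, favourable drift of 0.10 SD makes that test significant 29% / 31% / 41% of the time (n = 202 / 215 / 300). Adverse drift of 0.10 leaves a net 0.19 − 0.10 = 0.09 and cuts power from 77% / 79% / 91% to 25% / 26% / 34%.
3. **Minor.** Reconcile the between-group comparison at 3 and 9 months (Data Collection) with the use of the first three visits (Aims 1, 2 and 3(a)).

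**Cost.** Only plan wording and the choice of data rows change; there are no new visits. Sensitivity is lower. Detectable d at 80% power (two-sample t, two-sided 5%; adjusted values multiply by √(1 − r²), r = 0.5 to 0.3) is:

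| n | vs attention control (adjusted) | vs usual care (adjusted) | Unadjusted power at d = 0.19 |
|---|---|---|---|
| 215 | 0.43 (0.37–0.41) | 0.53 (0.46–0.50) | 24%, 17% |
| 300 | 0.36 (0.31–0.35) | 0.45 (0.39–0.43) | 31%, 22% |

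At n = 202 the unadjusted values are 0.44 and 0.55. The concurrent T2 analysis also stays open to confounding. With no causal path, a 0.3 SD gain and an assumed same-visit residual correlation of −0.1 or −0.2, it falsely shows mediation against attention control in 18% or 48% of trials at n = 215, and in 27% or 70% at n = 300.

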Limitations and Challenges. Our decision to limit participation to caregivers with computers and internet access is based on our pilot experience. In the ADRC pilot, we required participants to have their own computers and internet connection; we encountered very few problems. Access is not universal among caregivers, so results will not generalize to all caregivers, but, as noted, internet use in the target age groups (middle-aged and older) continues to rise.¹²⁸ We will employ easy-to-use platforms (Vidyo and Canvas) for Tele-Savvy and attention control conditions; both platforms are accessed by a simple click on an email-supplied link. Navigators can train caregivers to use Canvas and technical assistance of navigators will be provided (via phone and e-mail). A navigator will monitor all Tele-Savvy videoconferences to address any technical problems that might arise. We plan to conduct the videoconferences during weekday working hours; this may be a barrier for some eligible caregivers. To address this, we will schedule an occasional program on a weekend or in the evening. While recruitment is always a reasonable concern, our experience with the pilots provides confidence; operating with very little support, we were easily able to recruit 58 caregivers who completed the studies in the course of approximately 18 months. All of the collaborating sites were chosen because their recruitment bases are at least as strong as that at Emory. There were very few dropouts in the pilots among those who actually began the program (<10%); we have used a 25% attrition rate to be conservative in our estimates for our recruitment target.

References

1. Alzheimer's A. 2016 Alzheimer's disease facts and figures. *Alzheimers Dement*. 2016;12(4):459-509.
2. [name] K, Lewis M, Tornatore J, Sherman CW, Bremer KL. The Savvy Caregiver program: the demonstrated effectiveness of a transportable dementia caregiver psychoeducation program. *J Gerontol Nurs*. 2007;33(3):30-36.

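### The sample size rests on 20% attrition in one section and 25% in another, with no time horizon, an arm breakdown that does not sum and two enrolment targets

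*Combined protocol and SAP*

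**What the plan says.** Power Analysis and Sample Size Determination states the target as "we will enroll 270 CGs (108 for TS and AC groups and 54 for UC group"), "allowing for an expected 20% attrition". The number expected to remain is introduced there as "With a final expected sample size of 215 (86, 86, 54 in Tele-Savvy (TS), attention control (AC), and usual care (UC) groups respectively").

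That 215 supports three calculations in the section:
- the three-group test over T1, T2 and T3, with detectable f of 0.21 to 0.24;
- the pooled pre-post test, which takes T1 to T3 from the immediate group and T3 to T5 from both control groups, and which "will yield a total estimated 215 subjects to perform a pre-post test to detect a small effect size of $d=0.19" (80% power, 5% level);
- the exploratory comparison by race and ethnicity.

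The section also sets the pooled sample against a cited range of 148 to 196 for mediation.

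Limitations and Challenges reports pilot experience, "There were very few dropouts in the pilots among those who actually began the program (<10"%), and then says "we have used a 25% attrition rate to be conservative in our estimates for our recruitment target".

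The Design section says "We aim to enroll 375 subjects in 25 cohorts of 15 subjects each", with "participants randomly assigned on a 2:2:1 ratio", but keeps arm sizes of 108, 108 and 54. The Aims and the project timeline have 18 cohorts of 15, which is 270. Data Collection places the follow-up visits at months 3, 6, 9 and 12, so T3 is month 6 and T5 is month 12.

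**The concern.** Two sections describe the same sizing step with different loss rates. A reader of Limitations and Challenges would believe that the target carries a margin for 25% loss. If 25% is meant as a loss rate, 270 enrolled does not contain that margin.

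The horizon matters because the control groups contribute to different analyses at different times. They need to reach month 6 for the randomised comparison, but month 12 to contribute fully to the pooled pre-post effect and the sustained mediation analysis. They are 162 of the 270 (60%). One retained number can serve both only if it is the month-12 number, or if no control caregiver is lost after month 6. The plan does not say which it is.

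At stake are the stated n, f and d, and the mediation sample. The validity of the comparison itself is not affected.

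**Working it through.** **Inputs.** From the power section: 270 enrolled (108/108/54), 20% attrition, 215 expected, 80% power, 5% level, f of 0.21 to 0.24, d of 0.19. From Limitations and Challenges: 25%. From Design: 375. Two-sided testing is assumed, since sidedness is not stated.

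**1. Reproducing 215.**
- 270 × 0.80 = 216, and 215 / 0.80 = 269. The plan's figures follow from a 20% loss.
- By arm: 108 × 0.80 = 86.4 and 54 × 0.80 = 43.2. So 86 + 86 + 43 = 215.
- The printed breakdown gives 86 + 86 + 54 = 226. Usual care is left at its enrolled size, with no attrition applied.

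**2. Reproducing the detectable effects at 215.**
- Pooled test, normal approximation: d = (1.960 + 0.842) / √215 = 0.191. The paired t-test with the noncentral t gives 0.192, and power at d = 0.19 is 79.2%. This agrees with the stated 0.19.
- Three-group test, noncentral F with λ = N f²: f = 0.213 (group), 0.212 (time), 0.237 (interaction). This agrees with 0.21 to 0.24. The λ convention is inferred from this match; the alternative that uses the within-person correlation gives 0.09 to 0.17 and does not match.
- At 226 the same formula gives 0.207 to 0.231, which rounds to 0.21 to 0.23. The stated range therefore points to 215, and the 54 looks like the slip.

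**3. Putting 25% in as a loss rate.**
- 270 × 0.75 = 202.5, or 81/81/40.5 by arm.
- Keeping 215 would need 215 / 0.75 = 286.7, so 287 enrolled.
- At 202: d = 0.198, power at d = 0.19 is 76.7%, and f is 0.219 to 0.245.

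**4. Putting 25% in as an add-on.** 215 × 1.25 = 268.75 and 216 × 1.25 = 270. An inflation of 25% on the final number is the same design as a 20% loss.

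**5. Horizon.** Suppose 20% is the loss by month 6, leaving 86 immediate and 129 control caregivers, and a further fraction x of controls is lost by month 12. Then pooled n = 86 + 129 × (1 − x). The values of x below are an assumed range; the documents give none.

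| Further control loss x | Pooled n | Detectable d | Power at d = 0.19 |
|---|---|---|---|
| 0 | 215 | 0.192 | 79.2% |
| 5% | 209 | 0.195 | 78.1% |
| 10% | 202 | 0.198 | 76.7% |
| 20% | 189 | 0.205 | 73.9% |

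If 20% is instead the loss by month 12, the pooled n is 215 as stated, and 215 is conservative for the month-6 test.

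**6. Enrolment.** 18 × 15 = 270 and 25 × 15 = 375. From 375, a 20% loss leaves 300 and a 25% loss leaves 375 × 0.75 = 281. Neither is 215.

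**The case against.** The strongest reply is that the 25% is a mislabelled add-on. Step 4 shows that the arithmetic fits, and on that reading the design is sound and only one sentence is wrong. This is plausible, but the text calls the figure an attrition rate and nothing in the documents supports the other reading. The sentence needs correcting either way.

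A reader might also infer that using 215 at both horizons is a contradiction, so that the planning numbers cannot all hold. The documents do not support that. If 20% is loss by month 12, the pooled figure is right and the month-6 test merely has a little in hand. What stands is the missing horizon. The pilot's low dropout does not supply one, because it covers a six-week programme with questionnaires within two weeks of its end.

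A further reply is that the mixed models use all available data and that the immediate effects need controls only to month 9. That is correct, and it softens the loss for those analyses. It does not cover the mediation analysis or the ANCOVA by race and ethnicity, for which no missing-data method is stated. Nor does it help with a control lost before the T3 visit, who has no T3 to T5 data to contribute.

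Finally, the Design section's 375 would leave 281 even at 25%, more than 215. That stands: any shortfall is shown only for the 270 design. The Design section also refers to a separate Amendment 8 document, not among the material reviewed, which may explain the 375.

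**Conclusion.** The attrition figures disagree as written, and only 20% as a loss rate reproduces 215 from 270. The horizon for that loss is unstated, the arm breakdown sums to 226 instead of 215, and 270 and 375 are both given as the enrolment target.

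The size is modest. With 270 enrolled and a true 25% loss, the retained number falls by about 13, d rises from 0.192 to 0.198 and f by less than 0.01. If 20% is the month-6 loss and a further 5% to 20% of controls leave later (assumed), the pooled n is 209 to 189 and d is 0.195 to 0.205.

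It would be tempting to conclude that the trial is underpowered or that the mediation sample is inadequate. Neither follows. The numbers computed here, 189 to 209, lie within or above the range of 148 to 196 that the plan itself cites as adequate, and a target of 375 would remove the shortfall. The defect is that a reader cannot tell which planning numbers apply. The figures assume two-sided testing and the λ convention that reproduces the plan's own f.

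**What to change.** - State one enrolment figure and use it in the Aims, Design, timeline and power section. If 375 is current, restate the arm sizes too (150/150/75 at 2:2:1).
- State one attrition rate and say whether it means loss by month 6 or by month 12. Amend Limitations and Challenges or the power section so that they agree. If 25% was an add-on to the final number, say so.
- Correct the breakdown of 215 to 86/86/43 if 270 and 20% are kept.
- Give the expected number by arm at T3 and at T5. Compute f for the three-group test from the T3 numbers. For d and the sustained mediation analysis, use T3 for the immediate group and T5 for the controls. Apply the matching number to the race and ethnicity comparison as well.

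The cost is a text correction and a rerun of the power calculations. No extra enrolment or design change is needed. The only downside is slightly less favourable stated figures if 25%, or later loss of controls, applies.
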